1.0 Project Summary/Abstract

- This is a multi-center, randomized interventional clinical trial with a 2x2 crossover design of patients with keratoconus fit with corneal and scleral gas permeable contact lenses.
- While both corneal gas permeable and scleral lenses have been shown to improve visual acuity in individuals with keratoconus, it has yet to be determined if one option has superior comfort and overall patient satisfaction in patients new to gas permeable lens use.

2.0 Background/Scientific Rationale

- Keratoconus is a non-inflammatory, progressive disease in which corneal irregularity increases and thickness decreases. It is thought to occur in approximately 1 of 2,000 individuals¹ and has been associated with contact lens wear, eye rubbing, Down's syndrome, atopic disease, connective tissue disease, and family history of corneal ectatic disease.² As the condition develops, progressively more advanced forms of optical correction are needed to provide functional visual acuity for patients. Until recently, corneal rigid gas permeable lenses were considered the primary mode of correction for patients with keratoconus. Now, however, practitioners have multiple options for reducing the optical aberrations caused by keratoconus, including custom hydrogels, hybrid lenses, and scleral lenses. As a consequence patients who previously could not be fit with lenses are able to wear them, decreasing the need for surgical intervention such as keratoplasty. However, being able to use non-surgical strategies for keratoconus management may lead to an increased number of visits and complexity of decision-making during the contact lens fitting process. As of yet, no single option for optical correction has been identified as the preferred mode of correction in terms of overall patient satisfaction with vision, comfort, and ease of use. The order in which various forms of optical correction would be most logically introduced has yet to be determined.
- Keratoconus is known to impact overall quality of life, as well as vision-related quality of life.³⁻⁵ We hypothesize that patient-reported quality of life may vary depending upon the prescribed form of contact lens correction. Most studies, which investigate quality of life, are relatively small, and assess change in quality of life following a specific intervention.
- In this study, patients will be prospectively fit with both corneal gas permeable and scleral lenses according to standard clinical practice. Both corneal gas permeable and scleral lenses are considered standard of care for patients with keratoconus. In a previous study by Kumar et al, patients with keratoconus who were naive to contact lens wear reported comparable improvement in visual function (including logMAR acuity, contrast sensitivity function, stereoacuity using Howard-Dolman apparatus and higher-order wavefront aberrations) for both corneal gas permeable and scleral lenses.⁶ The authors suggest that non-visual factors such as quality of lens fitting, wearing comfort and cost may be more important for determining lens preference among patients than visual performance. Corneal gas permeable lenses were more difficulty to fit, and were not as comfortable, but were less expensive than scleral lenses.⁶

An additional study evaluated subjective comfort between corneal gas permeable and scleral lenses in patients with keratoconus who were stable corneal gas permeable lens users.⁷ Subjective comfort scores were significantly higher in

scleral lens wearers, however the final lens of choice in the study were similar with 53% opting to continue with their habitual corneal gas permeable lens and 47% choosing the scleral lens instead.⁷ Similar to the study by Kumar et al., there was no significant difference in best corrected visual acuity or contrast sensitivity function between the two lens modalities.⁷

3.0 Objectives/Aims

- Specific Aim;
- This study will prospectively compare visual satisfaction and ease of use between corneal gas permeable and scleral lenses for patients with mild to moderate keratoconus who are naïve to lens use.

- Hypotheses to be tested:
 1. Participants will select scleral lens over corneal gas permeable lens as their preferred final lens type. Scleral lens comfort will be rated higher than corneal gas permeable lenses.

- Primary Outcome Measure:
 1. The Primary outcome of this study is participant selected final lens choice for continued use for the management of keratoconus.

- Secondary Outcome Measures:
 1. Best corrected Snellen visual acuity converted to logMAR
 2. Practitioner ease of lens fitting including number of visits, number of trial lens required for fitting and number of lenses ordered.
 3. Patient burden including time required to learn safe application and removal as well as daily time require for lens application and removal.
 4. Subjective comfort with lens use rated on comfort scale of 0 (not comfortable) to 10 (very comfortable)
 5. Dry eye symptoms assessed using the validated OSDI and CLDEQ do we get baseline meibography on each patient.
 6. Impact of lens cost on lens choice.

Methods:

- Patients will be consented and enrolled in the study during routine clinical visits.
- At the first study visit, participants will be fit with corneal gas permeable and scleral lenses in both eyes. The OSDI and CLDEQ questionnaires will be assessed.
- The patient will return for regularly scheduled fitting visits to maximize lens fitting and visual acuity.
- At the 2nd study visit, patients will be randomized to receive lens application and removal training with lens type #1. Patients will begin daily wear of lens type #1.

- At the 3rd study visit (2-4 weeks after dispensing of lens #1), visual acuity, ease of use and subjective comfort of lens #1 will be assessed. The OSDI and CLDEQ questionnaires will be repeated.
- The participant will be trained in lens application and removal with lens #2. Lens #1 will be returned to the study clinician unless the patient refuses (thus ending the study).
- At the 4th study visit (2-4 weeks after dispensing lens #2), visual acuity, ease of use and subjective comfort of lens #2 will be assessed. The OSDI and CLDEQ questionnaires will be repeated. Participants will be asked to select their final lens of choice. Participants unable to return for a study visit will be contacted to complete the surveys and final lens preference,

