- Final participant preferences- participants can be contacted to complete the surveys and final lens preference,
 - .1 Dry eye symptoms assessed (OSDI questionnaire), contact lens comfort assessed (CLDEQ). [for research purposes]
 - .2 Participant final selection of lens of choice #1 or #2 [for research purposes].
 - .3 Participant final selection of lens of choice #1 or #2 given average self-pay cost of annual replacement [for research purposes].
- Unscheduled visits
 - Will tally unscheduled visits and current lens type. [standard of care]

For Studies that Collect Prospective Data

- Data will be collected prospectively from the electronic medical record using paper care report forms and RedCAP by the primary and co-investigators at all study sites.
- A master list will be used to code participants and maintain study documents with study ID only. The list will be maintained by the investigator at each study site. De-identified data only will be shared with co-investigators listed on the study and with the locations listed on this study. The list will be stored in a locked cabinet of a locked office.
- At the completion of the study, the lists will be destroyed.
- De-identified data only will be maintained for future research use.

Survey studies

- Participants will complete the validated 12-item OSDI¹⁰ and the Contact lens dry eye questionnaire-8 (CLDEQ-8)¹¹ and comfort scale of contact lens performance to assess dry eye symptoms at each study visit.
- The OSDI Score is assessed on a scale of 0 to 100 with higher scores representing greater disability.

Studies involving use of product

- Two products will be used in this study.
 - Contact lens #1: SynergEyes VS (Synergeyes, Inc., Carlsbad CA) which features bi-tangential toric peripheries with linear landing zones. The standard lens is 16.0mm and is available from 14.5 to 17.5mm diameters.
 - Contact lens #2: RoseK2 corneal gas permeable lens (Blanchard Contact Lens, Inc. Manchester, NH). The lens is available in with a base

Initial correction keratoconus: corneal gas permeable vs scleral lens

curve range from 4.30 to 8.60 mm, diameter of 7.90 to 10.40mm.

- Product information including lens order number, lens parameters, lens materials and verification will be tracked and maintained in the case report form and on RedCAP.
- Adverse events will be recorded and immediately reported to the clinic PI.

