9.0 Data Analysis

- Final lens selection will be calculated for each randomization group.
- Descriptive statistics will be used to compare logMAR visual acuity, comfort (OSDI and CLDEQ) and number of lenses ordered to achieve fitting for lens #1 and lens #2. Meibography will be analyzed.

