 - .1 *Best corrected visual acuity with lens #1*
 - .2 *Hours of lens wear today, average hours of lens wear time, days per week of per week and daily time spent on lens application and removal*
 - .3 *Subjective comfort with lens use rated on comfort scale of 0 (not comfortable) to 10 (very comfortable)*
 - .4 *OSDI questionnaire*
 - .5 *CLDEQ questionnaire*
 - .6 *Time started/finished application and removal handling*
 - .7 *Best corrected visual acuity with lens #2*
 - .8 *Subjective comfort with lens use rated on comfort scale of 0 (not comfortable) to 10 (very comfortable)*
- *Study visit number 4*
 - .1 *Best corrected visual acuity with lens #2*
 - .2 *Hours of lens wear today, average hours of lens wear time, days per week of per week and daily time spent on lens application and removal*
 - .3 *Subjective comfort with lens use rated on comfort scale of 0 (not comfortable) to 10 (very comfortable)*
 - .4 *OSDI questionnaire*
 - .5 *CLDEQ questionnaire*
 - .6 *Participant final selection of lens of choice #1 or #2*
 - .7 *Participant final selection of lens of choice #1 or #2 given average self-pay cost of annual replacement.*

Non-study visits

Lens #1- number of lenses needed to finalize

Lens #2- number of lenses needed to finalize

Unscheduled visits

.1 Study ID

Date

Reason for unscheduled visit

Lens type unscheduled visit is related to (corneal gas permeable or scleral lens)

Lens loss

Lens breakage

Other problem (describe)

Len cessation advised? Yes/No

Adverse Event reporting

Study ID

Date

Type of adverse event:

Medical treatment required:

Len cessation advised? Yes/No

Questionnaires

OSDI 12

CLDEQ-8

Initial correction keratoconus: corneal gas permeable vs scleral lens

Ocular Surface Disease Index[®] (OSDI[®])²

Ask your patients the following 12 questions, and circle the number in the box that best represents each answer. Then, fill in boxes A, B, C, D, and E according to the instructions beside each.

Have you experienced any of the following during the last week ?	All of the time	Most of the time	Half of the time	Some of the time	None of the time
1. Eyes that are sensitive to light? . .	4	3	2	1	0
2. Eyes that feel gritty?	4	3	2	1	0
3. Painful or sore eyes?	4	3	2	1	0
4. Blurred vision?	4	3	2	1	0
5. Poor vision?	4	3	2	1	0

Subtotal score for answers 1 to 5

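### Refusing to hand back lens #1 at visit 3 ends the study, but the primary outcome is requested only at visit 4 or by later contact, so these choices may be lost

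*Protocol*

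**What the plan says.** Section 3.0 makes the primary outcome the "participant selected final lens choice for continued use for the management of keratoconus". The Methods list in the same section describes the exchange at visit 3: the participant is trained on lens #2, and "Lens #1 will be returned to the study clinician unless the patient refuses (thus ending the study".

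The outcome is requested at these points:

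- **Visit 4.** Section 3.0 (Methods) says of this visit that "Participants will be asked to select their final lens of choice". Section 6.0 and the visit 4 form in Appendix B list the choice there too. They add a second item: "Participant final selection of lens of choice #1 or #2 given average self-pay cost of annual replacement".
- **Contact route, Section 3.0.** "Participants unable to return for a study visit will be contacted to complete the surveys and final lens preference".
- **Contact route, Section 6.0.** Under final participant preferences, "participants can be contacted to complete the surveys and final lens preference".

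Neither the visit 3 procedures in Section 6.0 nor the visit 3 form in Appendix B contains a preference item or a place to note that the exchange was refused. Appendix B has forms for the four visits, non-study visits, unscheduled visits and adverse events, but none for withdrawal or end of study.

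For analysis, Section 9.0 says "Final lens selection will be calculated for each randomization group". Sections 6.0 and 12.0 describe a descriptive pilot, meant to inform the sample size and feasibility of a larger trial.

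**The concern.** Keeping lens #1 at visit 3 comes close to being the primary outcome, observed early. The protocol treats it as an exit and places the outcome question after the exit. If the choice is not captured, the data are missing because of their own value: each sequence group loses people who favour the lens it received first.

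Three results are at stake:

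- **Choice by randomization group.** This is the summary Section 9.0 asks for. Each group's share is pushed away from its first-dispensed lens, which would read as an order effect.
- **Choice given self-pay cost.** This item is lost along with the primary outcome, which affects the secondary outcome on lens cost.
- **Number of refusals.** For a feasibility pilot this is a finding in its own right, and no form is designed to count it.

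**Working it through.** **Is there a step that is sure to capture a refuser's choice?**

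| Step | Covers a visit 3 refuser? |
|---|---|
| Visit 3 procedures and form | No choice or refusal item |
| Visit 4 | Not reached; the study has ended for that person |
| Contact route, Section 3.0 (will be contacted) | Written for those unable to return; a refuser attended |
| Contact route, Section 6.0 (can be contacted) | Permitted but optional; refusers not named |

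So capture is possible but not assured.

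**Inputs.** From the protocol: five sites of up to 25 give 5 × 25 = 125, which reproduces the stated maximum. Allocation by odd or even study ID is about 1:1, so 62.5 per sequence. The protocol gives no refusal rate and no expected preference for this population, so the following are assumptions:

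- *p*: true scleral share, the same in both sequences (no real order effect)
- *rs*, *rc*: refusal among scleral-preferrers given scleral first, and among corneal-preferrers given corneal first
- *q*: refusal among those who would have ended on lens #2

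**Refusers left out.**

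- Scleral-first share = p(1−rs) / [p(1−rs) + (1−p)(1−q)]
- Corneal-first share = p(1−q) / [p(1−q) + (1−p)(1−rc)]
- With q = 0, choices lost = 62.5 × [p·rs + (1−p)·rc]

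With p = 0.65, q = 0 and equal refusal:

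| rs = rc | Scleral-first | Corneal-first | Lost of 125 | Pooled |
|---|---|---|---|---|
| 10% | 0.585/0.935 = 62.6% | 0.650/0.965 = 67.4% | 6.25 | 65.0% |
| 20% | 0.520/0.870 = 59.8% | 0.650/0.930 = 69.9% | 12.5 | 65.0% |
| 30% | 0.455/0.805 = 56.5% | 0.650/0.895 = 72.6% | 18.75 | 65.0% |

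With rs = rc = r the pooled share is p(2−r−q) / (2−r−q) = p. It is therefore unbiased when refusal is equal.

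With unequal refusal it is not:

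- rs = 30%, rc = 10%: (0.455 + 0.650) / (0.805 + 0.965) = 62.4%
- rs = 10%, rc = 30%: (0.585 + 0.650) / (0.935 + 0.895) = 67.5%

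**Dependence on p.** The only preference figure in the protocol is 47% scleral, from a cited study in established corneal lens wearers (Section 2.0). At p = 0.47 and 20% refusal the shares are 0.376/0.906 = 41.5% and 0.470/0.894 = 52.6%, a gap of about 11 points. The between-group distortion hardly depends on p.

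**Refusal as a share of the whole sequence group.** Write this as fS (scleral-first) and fC (corneal-first). The pooled recorded share is (p − fS/2) / [1 − (fS + fC)/2]. At p = 0.60:

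- fS = 20%, fC = 0: 0.50/0.90 = 55.6%
- fS = 0, fC = 20%: 0.60/0.90 = 66.7%

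In the scenarios run over p = 0.5 to 0.7 and 0 to 20% refusal per order, the error ran from −5.6 to +7.8 points.

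**Refusers counted as choosing lens #1.** Some refusers might have switched after wearing lens #2. The scleral-first share is then p + (1−p)q, the corneal-first share is p(1−q), and the gap equals q. With rs = rc = 20% and q = 5%:

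| Handling | Scleral-first | Corneal-first | Gap (points) |
|---|---|---|---|
| Counted as lens #1 | 66.75% | 61.75% | +5.0 |
| Left out | 0.520/0.8525 = 61.0% | 0.6175/0.8975 = 68.8% | −7.8 |

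The true gap of zero lies between the two.

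**The case against.** The strongest reply is that the act itself reveals the choice. The clinician sees the refusal, the participant receives the chosen lens free (Section 5.0), and lens orders are tracked, so the site would normally know which lens was kept. The Section 6.0 contact route is also open to anyone. This makes an irrecoverable loss less likely. It does not give a recorded choice, a reason or a choice given cost, and what a site happens to know is not a data item.

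A second reply is that counting rules and analysis sets belong in the SAP, which was not available here. That is fair as far as it goes, and silence on those rules is not the fault raised. The fault is in data collection: a SAP can say how to count a refuser but cannot recover an answer that was never requested.

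A third is that the effect is assumed and modest. Willingness to attend four visits is required and payment comes at completion, so refusal may be rare. Section 3.0's hypothesis concerns the overall choice. There, equal refusal causes no bias and 30% against 10% shifts the share by about 2.5 points, against a standard error of about 4.3 points (√(0.65 × 0.35/125)). The 10-point between-group gap is close to one standard error (about 9 points with some 56 per group). This stands as a limit on size. It does not make the bias disappear, and a descriptive analysis offers no protection from it.

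Finally, counting refusers brings an error of its own, as the last table shows. That is a reason to report both results, not to leave the choice uncollected.

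**Conclusion.** The concern holds as a gap in outcome capture. A stated exit rule removes participants because of their lens preference, before the protocol is sure to ask for it. The claim is that these choices may be lost, not that they must be.

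Under the assumed rates (65% true scleral preference; 10% to 30% refusal among those whose preferred lens came first) about 6 to 19 of 125 choices go missing, and a false gap of roughly 5 to 16 points (67.4 − 62.6 to 72.6 − 56.5) opens between the sequence groups. The pooled share is distorted only if refusal differs between people who prefer scleral and people who prefer corneal lenses. The documents give no basis for a direction. All sizes rest on assumed rates, full enrolment of 125 and an equal split. The weakness is easy to repair and should be repaired before enrolment, because answers not collected at visit 3 may not be recoverable.

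**What to change.** On the visit 3 form in Appendix B, and in the visit 3 list in Section 6.0, add fields completed before the study ends for a participant who declines the exchange:

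- that the exchange was refused, and why
- the stated final lens choice
- the stated choice given self-pay cost

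Record the choice by lens type. Lens #1 means the first-dispensed lens in Section 3.0 but the scleral product in Section 6.0.

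In Section 3.0, add a sentence saying that this choice counts for the primary outcome in the participant's assigned sequence group. Report beside it the result restricted to participants who wore both lenses, together with the number of refusals by sequence.

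The cost is a sentence and a few form fields. No lens, schedule or clinical rule changes, and participants remain free to refuse. The drawback is that refusers choose without daily wear of lens #2, so counting them can overstate the first lens in each group. That is why both results are needed.

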4.0 Eligibility

- Potential participants will be identified and recruited from ophthalmology and optometry clinics at study sites during routine visits.
- Individuals must have a diagnosis of keratoconus confirmed by clinical examination and topography.
- Williness to return for a minimum of 4 study visits.
- The principal and co-investigators will determine subject eligibility using study eligibility checklist.

4.1 Inclusion Criteria

- Age 18 or older.
- Diagnosis of keratoconus.
- Available baseline corneal topography and pachymetry.
- Amsler-Krumeich keratoconus classification⁹ of stage 1 or higher

Table 1 Standard Amsler-Krumeich keratoconus classification.

Stage I	Eccentric steepening Myopia/astigmatism < 5.00 D Mean K < 48.0 D
Stage II	Myopia/astigmatism > 5.00 D but < 8.00 D Mean K < 53.0 D Absence of scarring Minimal apical corneal thickness > 400 µm
Stage III	Myopia/astigmatism > 8.00 D but < 10.00 D Mean K > 53.0 D Absence of scarring Minimal apical corneal thickness < 400 µm but > 300 µm
Stage IV	Refraction not possible Mean K > 55.0 D Central corneal scarring Minimal apical corneal thickness < 300 µm

4.2 Exclusion Criteria

- No prior corneal transplantation or INTACTS.
- No prior use of hybrid, corneal or scleral gas permeable lenses.
- Presence of corneal scarring.

4.3 Excluded or Vulnerable Populations

- No vulnerable populations will be enrolled.
- Non-English speaking subjects can be enrolled with the use of translation services.

5.0 Subject Enrollment

- After identification, potential participants will be asked if they would like to hear more about the study during routine clinical visits.
- A standardized recruitment script will be used by study investigators.
- The informed consent document will be reviewed with potential participants.
- Individuals with a diagnosis of keratoconus meeting all inclusion and exclusion criteria and willing to participate will be enrolled by the principle and co-investigators.
- Participants will be compensated \$40 (Visa gift cards) for each of the four study visits at the completion of the study. The patient will receive their final selected lens of choice at no cost.

6.0 Study Design and Procedures

- Multi-center study sites will include:
 - .1 Illinois Eye and Ear Infirmary, Chicago IL.(UIC)
 - .2 Millennium Park Eye Center, Chicago, IL. (UIC)
 - .3 The Mayo Clinic, Rochester MN.
 - .4 The Ohio State University, Columbus OH.
 - .5 The Illinois College of Optometry, Chicago IL.

- This is a prospective, multi-center, randomized interventional clinical trial with a 2x2 crossover design of patients with keratoconus fit with corneal and scleral gas permeable contact lenses. The crossover design allows intra-subject differences between two randomized groups with participants serving as their own controls.
- This is a pilot study to determine sample size and feasibility of study protocol for a larger randomized study.
- Each clinic will enroll up to 25 participants with a maximum of 125 participants.

- Screening eligibility
 - .1 Patients age 18 or older with a diagnosis of keratoconus will be recruited during routine clinical exams at the Illinois Eye and Ear Infirmary.
 - .2 Available baseline corneal topography and pachymetry.
 - .3 Willingness to return for 4 study visits.
- Informed consent will be obtained by the principal investigator or co-investigators.

- Study visit number 1 (estimated 45-90 minutes)
 - .1 Patient demographics (age, race, age diagnosed with keratoconus) [standard of care]
 - .2 Past ocular and medical history including ocular procedures such as corneal collagen crosslinking and corneal surgery. [standard of care]
 - .3 Best corrected visual acuity with manifest refraction [standard of care]
 - .4 Corneal curvature using topography [standard of care]
 - .5 Corneal pachymetry (thickness) [standard of care]
 - .6 Meibography [standard of care] if already performed and present in the patient's medical record, the data will be gathered. However, it will not be completed solely for the purpose of this study. .

 - .7 Dry eye symptoms and contact lens comfort assessed using the validated 12-item OSDI and CLDEQ questionnaire. [for research purposes]
 - .8 Research intervention: Fitting for keratoconus [standard of care]
 - .8.1 Both eyes will be fit according to standard practices with the RoseK 2 corneal gas permeable and Synergeyes VS scleral lenses following manufacturer's recommendations.

.8.1.1 Over refraction and best corrected visual acuity.

.8.1.2 Subjective comfort with lens use rated on comfort scale of 0 (not comfortable) to 10 (very comfortable).

- Routine Follow up visits to evaluate lens fit and visual acuity according to standard practice until lenses are deemed adequate for dispensing. [standard of care].
- Study visit number 2 (estimated 30-60 minutes)
 - .1 Randomize to dispense lens #1 vs lens #2. [for research purposes]
 - .2 Lens application and removal handling [standard of care].
 - .3 Instructions on lens disinfection procedures.
 - .4 Best corrected visual acuity with lens #1 [standard of care]
 - .5 Subjective comfort with lens use rated on comfort scale of 0 (not comfortable) to 10 (very comfortable) [for research purposes].
- Study visit number 3- wearing lens #1 between 2-4 weeks for minimum of 3 hours (estimated 45-75 minutes)
 - .1 Best corrected visual acuity with lens #1 [standard of care]
 - .2 Hours of lens wear today, average hours of lens wear time, days per week of per week and daily time spent on lens application and removal (general question – patients will not need to keep track or a log) [standard of care]
 - .3 Subjective comfort with lens use rated on comfort scale of 0 (not comfortable) to 10 (very comfortable) [for research purposes].
 - .4 Dry eye symptoms assessed (OSDI questionnaire), contact lens comfort assessed (CLDEQ). [for research purposes]
 - .5 Lens #2 application and removal training [for research purposes].
 - .6 Best corrected visual acuity with lens #2 [standard of care].
 - .7 Subjective comfort with lens use rated on comfort scale of 0 (not comfortable) to 10 (very comfortable) [for research purposes].
- Study visit number 4- wearing lens #2 between 2-4 weeks for minimum of 3 hours (estimated 15-45 minutes)
 - .1 Best corrected visual acuity with lens #2 [standard of care]
 - .2 Hours of lens wear today, average hours of lens wear time, days per week of per week and daily time spent on lens application and removal (general question – patients will not need to keep track or a log) [standard of care]
 - .3 Subjective comfort with lens use rated on comfort scale of 0 (not comfortable) to 10 (very comfortable) [for research purposes].
 - .4 Dry eye symptoms assessed (OSDI questionnaire), contact lens comfort assessed (CLDEQ). [for research purposes]

- .5 Participant final selection of lens of choice #1 or #2 [for research purposes].
- .6 Participant final selection of lens of choice #1 or #2 given average self-pay cost of annual replacement [for research purposes].
- Final participant preferences- participants can be contacted to complete the surveys and final lens preference,
 - .1 Dry eye symptoms assessed (OSDI questionnaire), contact lens comfort assessed (CLDEQ). [for research purposes]
 - .2 Participant final selection of lens of choice #1 or #2 [for research purposes].
 - .3 Participant final selection of lens of choice #1 or #2 given average self-pay cost of annual replacement [for research purposes].
- Unscheduled visits
 - Will tally unscheduled visits and current lens type. [standard of care]

For Studies that Collect Prospective Data

- Data will be collected prospectively from the electronic medical record using paper care report forms and RedCAP by the primary and co-investigators at all study sites.
- A master list will be used to code participants and maintain study documents with study ID only. The list will be maintained by the investigator at each study site. De-identified data only will be shared with co-investigators listed on the study and with the locations listed on this study. The list will be stored in a locked cabinet of a locked office.
- At the completion of the study, the lists will be destroyed.
- De-identified data only will be maintained for future research use.

Survey studies

- Participants will complete the validated 12-item OSDI¹⁰ and the Contact lens dry eye questionnaire-8 (CLDEQ-8)¹¹ and comfort scale of contact lens performance to assess dry eye symptoms at each study visit.
- The OSDI Score is assessed on a scale of 0 to 100 with higher scores representing greater disability.

Studies involving use of product

- Two products will be used in this study.
 - Contact lens #1: SynergEyes VS (Synergeyes, Inc., Carlsbad CA) which features bi-tangential toric peripheries with linear landing zones. The standard lens is 16.0mm and is available from 14.5 to 17.5mm diameters.
 - Contact lens #2: RoseK2 corneal gas permeable lens (Blanchard Contact Lens, Inc. Manchester, NH). The lens is available in with a base

Initial correction keratoconus: corneal gas permeable vs scleral lens

curve range from 4.30 to 8.60 mm, diameter of 7.90 to 10.40mm.

- Product information including lens order number, lens parameters, lens materials and verification will be tracked and maintained in the case report form and on RedCAP.
- Adverse events will be recorded and immediately reported to the clinic PI.
 - Potential adverse events include corneal scratch or abrasion related to lens handling, blurred vision, red or irritated eyes, pain in and around the eyes and excessive tearing.

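### The primary outcome is the lens chosen for continued use, but the item offers only #1 or #2, so it records relative preference and cannot show how many participants would continue neither lens

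*Protocol*

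**What the plan says.** Protocol section 3.0 (Primary Outcome Measure) defines the outcome as "participant selected final lens choice for continued use for the management of keratoconus". The hypothesis in the same section is comparative: "Participants will select scleral lens over corneal gas permeable lens as their preferred final lens type".

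Section 6.0, study visit 4, collects the outcome as "Participant final selection of lens of choice #1 or #2 [for research purposes". A second item adds price: "Participant final selection of lens of choice #1 or #2 given average self-pay cost of annual replacement [for research purposes". Both items recur with the same two options under the remote route for participants who cannot attend (6.0, Final participant preferences). The Appendix B form for visit 4 has "Participant final selection of lens of choice #1 or #2". No section offers a response for neither lens or asks about intention to go on wearing the chosen one.

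Section 5.0 adds that "The patient will receive their final selected lens of choice at no cost". The unscheduled-visit and adverse-event forms in Appendix B carry the field "Len cessation advised? Yes/No", which is not linked to the primary outcome. Section 9.0 tabulates final lens selection by randomization group. Sections 6.0 and 12.0 describe the study as a pilot for a larger randomized trial.

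**The concern.** An outcome defined as continued use has two parts: whether the person will go on with a lens, and which one. The item asks only the second. Participants are new to gas permeable lenses, and the protocol itself foresees handling problems, discomfort and stopping of lens wear, so declining both lenses is a possible answer. The free supply of the selected lens means that naming one costs nothing even to someone who will not wear it. Declining both is at least as plausible under the cost-framed item, which has the same two options.

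An analysis plan cannot recover a category that the form never collected. At stake is a feasibility quantity that a pilot should hand to the larger trial: the share of new wearers who accept neither lens. A shift in the preference split is a secondary risk.

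The option labels add a separate problem. Section 6.0 (Studies involving use of product) assigns #1 to the scleral product and #2 to the corneal product. In the visit 3 and visit 4 procedures, #1 and #2 are the first and second lens worn.

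**Working it through.** **1. Definition against response set**

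| Place | What it asks or allows |
|---|---|
| 3.0, primary outcome | Lens chosen for continued use |
| 3.0, hypothesis | Scleral preferred to corneal |
| 6.0, visit 4 (plain and cost-framed) | #1 or #2 |
| 6.0, remote contact (plain and cost-framed) | #1 or #2 |
| Appendix B, visit 4 (plain and cost-framed) | #1 or #2 |

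The response set matches the hypothesis but not the outcome definition.

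**2. What forced choice does to the figures**

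The only sample-size figure in the protocol is the maximum: 5 sites × 25 = 125, which reproduces. The other inputs are assumptions:
- q = share who would continue neither lens
- p = scleral share among those who would continue
- a = share of the neither group who name scleral when forced to choose

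Formulas:
- True continued scleral use over all participants = (1 − q)p
- Reported scleral share, if everyone answers = (1 − q)p + qa
- Shift of the head-to-head share from p = q(a − p)
- Sum of the two true continued-use shares = 1 − q; sum of the two reported shares = 100%

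With p = 0.55 and 125 answers:

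| Neither | Continued scleral use, all participants | Reported, even split | Reported, all name scleral | Reported, all name corneal |
|---|---|---|---|---|
| 12 (about 10%) | 0.55 × 113/125 = 49.7% | (62.15 + 6)/125 = 54.5% | (62.15 + 12)/125 = 59.3% | 62.15/125 = 49.7% |
| 25 (20%) | 0.55 × 100/125 = 44.0% | (55 + 12.5)/125 = 54.0% | (55 + 25)/125 = 64.0% | 55/125 = 44.0% |

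Against the head-to-head value of 55%, the shifts are −0.5, +4.3 and −5.3 points with 12 people, and −1.0, +9.0 and −11.0 points with 25.

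With p = 0.47, the scleral share in the cited study of habitual corneal lens wearers (section 2.0, illustration only), and q = 10%, true continued scleral use is 0.90 × 0.47 = 42.3%. The reported share can lie anywhere from 42.3% to 52.3%, depending only on how the neither group answers.

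For scale, the 95% confidence half-width at 50% with 125 responders is 1.96 × √(0.25/125) = 8.8 points.

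**3. If non-continuers leave the item blank**

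The share among responders is then p, with no shift. The number continuing neither is still unknown, because a blank for that reason looks like any other missing answer.

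**4. Labels**

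For a participant who starts with the scleral lens, #1 is scleral under both readings. For one who starts with the corneal lens, #2 means corneal by product and scleral by order, so the same recorded answer has opposite meanings. Appendix B starts odd study IDs with lens #1, so even IDs, roughly half the sample, are exposed.

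**The case against.** The strongest reply is that the protocol supports a comparative reading. The hypothesis is about preference, and sections 3.0 and 6.0 call the remote item a final lens preference. In a two-lens crossover, a two-option item answers that question directly. No section names an acceptance rate as an outcome. This stands to the extent that forced choice is a legitimate measure of relative preference; what remains wrong is that the primary outcome is worded as something else.

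A reader might infer that everyone who would stop both lenses is counted as choosing one. The protocol does not establish this. It does not say the item is mandatory, withdrawal is allowed at any time (section 11.0), and Appendix B lists fields rather than the built database form. Such participants may simply be missing.

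A reader might also infer a bias of 5 to 10 points from comparing 49.7% with 54.5%, or 44.0% with 54.0%. Most of that gap is a change of denominator, from all participants to those choosing a lens. The head-to-head share itself moves by only 0.5 to 1.0 points with an even split.

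The field on advised cessation is also weak evidence of participants wanting neither lens. It records a clinician's advice, and nothing shows that the advice is permanent or covers both lenses. Visits 3 and 4 do collect wear hours, days per week and comfort, which gives some view of poor acceptance. It does not replace a direct answer about continuing.

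**Conclusion.** The mismatch holds: the outcome is defined as continued use, and the item captures relative preference between two lenses. The pilot therefore cannot report how many participants would continue neither, and any statement that a given percentage chose a lens for continued use would go beyond what was asked.

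The size cannot be fixed from the protocol, which gives no rate of continuing neither; the 10%, 20% and 55% used above are assumptions, and 125 is an enrolment ceiling rather than a count of responders. What follows without those values is that the two reported shares sum to 100% of responders while true continued use sums to 1 − q. A material shift in the head-to-head share needs both a sizeable q and answers leaning to one lens. The protocol supports neither a claim that this happens nor a claim that non-continuers are always counted.

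The double meaning of #1 and #2 is a distinct defect in the same item. Unless one convention is fixed, it could reverse recorded choices for participants who start with the corneal lens.

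Minor to moderate for a descriptive pilot.

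**What to change.** In section 6.0 (visit 4 and remote contact) and Appendix B:

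- Keep the two-way preference, but record it by product: corneal gas permeable or scleral.
- Add one question to both the plain and the cost-framed item, such as *Will you continue to wear this lens? yes/no*. A third option for neither lens would also serve.
- Report preference and continued use as separate results.

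The cost is one extra question per choice item. With a third option instead, slightly fewer answers would inform the head-to-head percentage; the yes/no question avoids that. If the sponsor intends only relative preference, the minimum change is to reword the primary outcome in section 3.0 accordingly and to name the products in the item. That would still leave the pilot without the acceptance figure.
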